## B- METHODOLOGY OF QUESTIONNAIRES / INTERVIEWS

AWARDING PROCEDURE	
Questionnaires administered by:
 
 Mail
 
 Internet
 
 Phone
 
 Face to face: during the IVT
 
 Other (explain, list) : .....
 
Questionnaire administered in:
 
 Once
 
 Several times (specify the number of awards): 2
 
Questionnaire type:
 
 Validated
 
 Invalid
 
– if validated, indicate the origin of the validation:
 
For assessment of psychological state and anxiety before the intervention: HAD Anxiety Scale (Hospital Anxiety and Depression Scale - Authors: AS Zigmond and RP Snaith - French translation JL Lépine)
 
For pain assessment: Analogue Visual Scale (EVA): ranging from 1 to 10 cm
 
For assessment of pain relief: Simple verbal scale.
 
– if not validated, justify:
 
Does the research also involve collecting retrospective data:

---------------------------	---

	
 yes
 
 No
 
– if yes, justify:
 
The number of previous IVTs, the pathology requiring the IVT, eye treatments, allergies, history of eye surgery, use of oral analgesics will be collected by the nurses from the patients' medical files.

INTERVIEW	
Methods of realization :
 
 Individual interview
 
 Collective interview
 
Interview carried out in:
 
 Frontface to face during the IVT session
 
 video conference
 
 phone
 
 Other (explain, list) :
 
Interview carried out:
 
 once
 
 several times
 
Number of awards: 2
 
Type of maintenance:
 
 directive
 
 semi-directive
 
 non directive
 
Registration:
 
 No       yes

STATISTICAL DATA ANALYSIS	
Pseudo-anonymized data will be collected on an Epi-data spreadsheet
 
The analysis will be carried out using the statistical analysis software: R version 3.4.4 (R-project)
 
Descriptive statistical analysis
 
The results will be presented:
 
 
- As mean +- sd (min; max) for quantitative variables
 
- As a percentage for qualitative variables
 
 
Main criterion:
 
Comparison of the score obtained during the 1st evaluation (with conventional anesthesia) with the score obtained during improved anesthesia: paired T-test
 
Other analyses:
 
Data that were found statistically correlated to the result:
 
 
- The psychological state of the patient[13.22]
 
 
Comparison of the scores obtained between the 2 evaluations of the psychological state (HAD scale): paired t-test
 
 
- The injection site [23]
 
- The number of prior IVTs[23]
 
- gender and age[24]
 
 
Comparison of pain scores according to potentially correlated factors: multivariate analysis

REFERENCES OF THE RESPONSIBLE BIOSTATISTICIAN	
Last name First Name : [name]
 
Address: Jules Verne West Ophthalmological Institute
 
Clinical Research Department
 
[name]

[contact]

Email: [[contact]](mailto:[contact])

V. - INFORMATION RELATING TO THE IMPLEMENTATION OF THE RESEARCH:

PLACES OF RESEARCH	
OphAlliance Ophthalmology Center:
 
- Ophthalmological Institute of the West Jules Verne Clinic [name]

PROVISIONAL RESEARCH TIMETABLE	
Start of study: Upon receipt of the opinion of the CPP
 
Duration of the inclusion period: 15 days (for phase 1 and for phase 2: these are the patients selected from the phase 1 cohort)
 
End of study report: August 2022

NUMBER OF INTERVIEWEES	
1st part: All patients who are called for an IVT over a period of 15 days and who have given their consent to participate in clinical research: approximately 300 patients
 
2nd part: patients who felt severe pain during IVT (VAS <math>\geq 4/10</math>) and who consent to test another protocol (estimate: 40 to 60 patients)

INCLUSION CRITERIA 1st QUESTIONNAIRE	
 
- Over 18
 
- Participants having all their capacities of discernment and being able to answer the questionnaires
 
- Patient summoned for an intravitreal injection of an anti-VEGF drug in liquid form (ranibizumab, afibercept, bevacizumab)
 
- Indication for injection: painless retinal pathology (age-related macular degeneration, retinopathy diabetic, macular edema on venous occlusion
 

	
retinal, neovascular membrane on high myopia, or other).
 
-Note information given to the patient and collection of signed non-objection

EXCLUSION CRITERIA 1st QUESTIONNAIRE	
 
- Persons cited in articles L.1121-6 to L.1121-8 of the CSP
 
- Patients not followed at the IOO Jules Verne or at the Hauts Pavés practice.
 
- Eye pain before the procedure
 
- Intravitreal injections performed with oftriamcinolone acetonide
 
- Intravitreal injections performed with a larger gauge needle (Ozurdex® or Iluvien ®)
 
- Intravitreal injections performed using a disinfectant other than povidone iodine
 
- Patients for whom the protocol with lidocaine gel in anesthesia is already used
 
- Any cortisone injection
 
- Any uveitic inflammatory pathology whether immunological or infectious
 
- Anyone under systemic treatment with cortisone or morphine and its derivatives
 

INCLUSION CRITERIA 2nd QUESTIONNAIRE	
 
- Patient with a VAS score during the 1st assessment: VAS <math>\geq</math> 4/10
 
- Patients who have given their consent to switch to the protocol with the addition of lidocaine gel (information letter provided and collection of non-objection)
 

EXCLUSION CRITERIA 2nd QUESTIONNAIRE	
 
- Eye pain before the procedure
 
- patient taking additional or different analgesic treatment compared to the evaluation of the 1st questionnaire
 
- Known allergy to lidocaine or any of the other ingredients of Ophtesic (hypromellose (E464) type 2910, sodium hydroxide (E524), hydrochloric acid (E507))
 
- Presence before IVT of the following symptoms: ocular redness, burning sensation, corneal pathology, headache.
 

DOES THE RESEARCH INCLUDE PEOPLE WITH NO CONDITION?	 No  yes

	All people included are people who have an appointment for an Intra Vitreous Injection (IVT)
PERSONAL RECRUITMENT PROCEDURES	All patients who made an appointment for an Intra Vitreous Injection (IVT) at the IOO Jules Verne during the recruitment period.
INFORMATION AND TRACEABILITY PROCEDURES FOR NON-OPPOSITION	
Patient information
 
Patients will be fully and fairly informed, in understandable terms, of the objectives of the study, the nature of the information collected, and their right to object at any time to the use of the data collected.
 
All this information appears on an information form given to patients during their preoperative consultation.
 
Patients will be informed of the following:
 
 
- Presentation of the research project
 
- The nature of the information that will be used for this research
 
- The recipient of the data
 
 
In accordance to European Regulation No. 2016/679/EU of April 27, 2016 (applicable from May 25, 2018) and the amended “Computers and Liberty” law of January 6, 1978, the patient benefits from the following rights:
 
 
- Right of access, rectification, portability and erasure of their data
 
- Right to limit the processing of their data
 
 
For legitimate reasons, the right to oppose the processing of data concerning them
 
Collection not opposed
 
Patients will have to stipulate if they agree that we use their answers to the questionnaires

DISADVANTAGES FOR PEOPLE INCLUDED IN THE RESEARCH	
The answers to a questionnaire during an IVT do not present a risk for the patient.
 
Evaluation of our current practice using a questionnaire

DESCRIPTION OF THE DIFFERENT ANESTHETIC EYE DROPS USED DURING IVT	
TETRACAIN 1 PER CENT THEA, eye drops in solution in single-dose container Tetracaine Hydrochloride[25]
 
Eye drops in solution, contains an active substance, Tetracaine®. This substance is a local anesthetic capable of penetrating certain parts of the eye such as the cornea and the conjunctiva.
 
This drug is indicated as a local anesthetic during various surgical procedures or various eye examinations.
 
The side effects listed below are from post-marketing experience with tetracaine. Since these effects were reported spontaneously by a population of indeterminate size, it is not possible to estimate their frequency precisely, which is therefore considered to be indeterminate.
 
 
- Immune system disorders
 
 
Hypersensitivity including erythema, pruritus.
 
 
- Eye conditions
 
 
Keratitis (including ulcerative keratitis), corneal erosion, corneal oedema, eye irritation, eye pain.
 
.
 
OXYBUPROCAINE THEA HYDROCHLORIDE 1.6mg/0.4ml, eye drops in a single-dose container Oxybuprocaine Hydrochloride [26]
 
Ophthalmic local anesthetic

	
Like all medicines, this medicine can cause side effects, although not everyone gets them.
 
 
- A few collapses with bradycardia have been exceptionally reported
 
- Possibility of transient tingling or irritation upon instillation.
 
 
OPHTESIC 20 mg/g. ophthalmic gel in single-dose container  lidocaine hydrochloride[27]
 
OPHTESIC is an anesthetic ophthalmic gel used during ophthalmic procedures.
 
According to the public drug database, the following side effects of lidocaine gel have been described with an unknown frequency:
 
 
- Conjunctival redness, changes in corneal epithelium, eye burning sensation, pitted corneal inflammation, corneal swelling
 

EXPECTED DURATION OF DATA COLLECTION BY INTERVIEW OR QUESTIONNAIRE FOR A PARTICIPANT	
The duration of the interview is estimated at: 5-10 minutes for each questionnaire.

TOTAL FORECAST DURATION OF RESEARCH PARTICIPATION FOR A PARTICIPANT IF DATA COLLECTION IS CARRIED OUT SEVERAL TIMES	
 
- 5-10 minutes for the 1st assessment
 
- 5-10 minutes for the 2nd assessment
 

MAXIMUM ESTIMATED TRANSPORT TIME FOR PARTICIPANTS	no transportation 1st questionnaire: the day of the IVT 2nd questionnaire: the day of the IVT
MAXIMUM ESTIMATED TRANSPORT TIME FOR PARTICIPANTS	no transportation 1st questionnaire: the day of the consultation, IVT or surgery 2nd questionnaire carried out: if the patient had a VAS score greater than or equal to 4 and switched to the so-called improved anesthesia protocol with lidocaine gel
NAME AND CONTACT DETAILS OF THE DATA PROTECTION OFFICER	
Last name First Name : [name]
 
Address: Jules Verne West Ophthalmological Institute        Clinical Research Department        [name]
 
Email: [contact]

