According to the HAS report[21]: "OPHTESIC 20 mg/g (lidocaine), ophthalmic gel in a single-dose container, does not provide any improvement in actual benefit (ASMR V) compared with anesthetic eye drops in the topical anesthesia during ophthalmic procedures. ". However, in our practice, patients who received topical anesthesia for IVT using anesthetic drops (Tetracaine® or Oxybuprocaine®), associated with a drop of lidocaine gel, report less pain, especially when placing the blepharostat.

The aim of this study, which includes two parts, is to better understand the prevalence of pain and its intensity during IVT and then to evaluate the effectiveness of the protocol using a drop of lidocaine gel on a targeted population (patients with a VAS score  $\geq 4/10$ ) in order to improve the management of patients complaining of severe pain during the injection.

We will first assess the perception of pain and its intensity during IVT using questionnaire 1. Once this step has been completed, we will suggest that the patients who have felt the most pain (VAS  $\geq 4/10$ ) and who have chosen to switch to anesthesia with lidocaine gel will again assess the pain felt with questionnaire 2.

The study will therefore consist of analyzing the responses to a survey carried out using 2 questionnaires offered during 2 IVT sessions for the same patient:

- **Quiz 1:** survey carried out in the context of anesthesia with the reference method
- **Quiz 2:** survey carried out during improved anesthesia (protocol to be evaluated): Tetracaine® or Oxybuprocaine® eye drops combined with a drop of lidocaine gel.

Pain being strongly correlated with the psychological state of the patient, and his degree of anxiety before the injection [13] , a psychological evaluation of the patient before the intervention will be carried out using the HAD Anxiety Scale (Hospital Anxiety and Depression Scale) by AS Zigmond and RP Snaith (French Translation JL Lépine) during the 2 questionnaires.

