### III – OBJECTIVES AND JUDGMENT CRITERIA

MAIN OBJECTIVE	The main objective of this study is to evaluate the relief provided by so-called "improved" topical anesthesia by the preoperative instillation of a drop of lidocaine gel in addition to a drop of the anesthetic Tetracaine® or Oxybuprocaine® in patients perceiving severe pain during IVT compared to the reference anesthesia protocol.
MAIN JUDGMENT CRITERIA	
EVA Score: The figure will be rounded to the nearest millimeter
 
Comparison of the pain score felt during the injection during the 1st evaluation (with conventional anesthesia) with the pain score obtained during improved anesthesia.

SECONDARY OBJECTIVES	
 
1- Confirmation of pain relief with the score obtained on the simple verbal scale
 
2- Description of the prevalence and intensity of pain experienced by patients during IVT
 
3- Description of the psychological state of the patient during a IVT and validation of score stability
 

	4- Evaluation of the security of the protocol
SECONDARY JUDGMENT CRITERIA	
 
1. Descriptive statistics of the verbal scale score
 
2. Descriptive statistics of pain scores recorded during pain assessment using VAS for IVT with conventional topical anesthesia
 
3. Descriptive statistics of the psychological state of the study population. Comparison of the scores obtained between the 2 assessments
 
4. Description of possible side effects
 

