#### IV. - ORGANIZATION OF THE STUDY:

##### A. - SYNTHETIC DESCRIPTION OF THE STUDY SCHEME

[figure not shown]
SYNTHETIC DESCRIPTION	
Monocentric study
 
1. Initial evaluation of the pain felt by patients during an intravitreal injection (IVT) as well as their psychological state before the intervention
 
The basis for this evaluation is a questionnaire completed by the participants before and after the injection.
 
It is composed :
 
 
- A psychological assessment (the HAD Anxiety Scale (Hospital Anxiety and Depression Scale - Authors: AS Zigmond and RP Snaith - French translation JL Lépine) completed by the patient before the IVT
 
- 2 measures for pain assessment using VAS:           
 
o One to assess the pain felt when placing the blepharostat
 
o The other to assess the pain felt when inserting the needle: answer given just after the IVT session.
 
 
 

------------------------------	---

	
2. Selection of patients who felt the most pain (EVA <math>\geq 4/10</math>) and proposal to pass with the protocol: a drop of Tetracaine® or Oxybuprocaine® and a drop of lidocaine gel. Evaluation of pain and relief of patients during IVT with so-called "enhanced" topical anesthesia.
 
The basis for this evaluation also consists of a questionnaire completed by the participants before and after the injection.
 
It is composed :
 
 
- A psychological assessment (HAD Anxiety Scale (Hospital Anxiety and Depression Scale - Authors: AS Zigmond and RP Snaith) completed by the patient before IVT
 
- Of 2 measures for the evaluation of pain using VAS: one to evaluate the pain felt when inserting the blepharostat and the other to evaluate the pain felt when inserting the needle: response performed immediately after the IVT session.
 
- An assessment of pain relief: Simple verbal scale (1 for placing the blepharostat and the other for inserting the needle)
 
 
The answers to the questionnaires will be collected by one of the nurses (TEC or ARC) and the ARC orthoptists and the anonymized data will be sent to the biostatistician of the clinical research department for analysis.

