DESCRIPTION OF THE PROCEDURE OF THE IVT	
The injection is performed in the operating room dedicated to IVT at the Jules Verne clinic
 
Anesthesia procedure: reference method:
 
-Instillation of a drop of topical anesthetic: Tetracaine® or Oxybuprocaine®

	
 
- Initial cleansing of the surface of the patient's periocular skin with povidone iodine scrub. Rinse with saline solution and dry with sterile compresses.
 
- Instillation on the conjunctiva of a drop of povidone iodine in a 5% ophthalmic solution. After 2 minutes.
 
- Instillation of 2 drops of anesthetic: Tetracaine® or Oxybuprocaine®
 
 
Anesthesia procedure: with lidocaine gel:
 
 
- Instillation of a drop of topical anesthetic: Tetracaine® or Oxybuprocaine®
 
- Initial cleansing of the surface of the patient's periocular skin with povidone iodine scrub. Rinse with saline solution and dry with sterile compresses.
 
- Instillation on the conjunctiva of a drop of povidone iodine in a 5% ophthalmic solution.
 
- Instillation of lidocaine gel drop
 
 
Procedure common to both anesthesia protocols
 
 
- Preparation of the syringe containing the product to be injected in a sterile manner by the operator as close as possible to the injection
 
- Placement of a sterile drape isolating the patient's eye
 
- Placement of a blepharostat so as to limit the risk of contact between the needle and the free edge of the eyelids or eyelashes.
 
- IVT between 3.5 and 4 mm from the limbus: slow injection of the product
 
- Slow needle withdrawal.
 

--	--

COURSE OF THE STUDY	
The research includes 2 parts:
 

- Evaluation of the prevalence of pain and its intensity during an IVT. Cohort: For 15 days: distribution of the information letter during the consultation to all patients requiring IVT

- Evaluation of the effectiveness of the protocol using a drop of lidocaine gel Cohort: patients experiencing pain requiring management (VAS score <math>\geq 4</math>) and who wish to switch to the enhanced anesthesia protocol

---------------------	--

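### Part 2 selects patients on a high first-session pain score and the main paired t-test starts from that same session, so regression to the mean can pass for relief

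*Combined protocol and SAP*

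**What the plan says.** **Entry to part 2.** Section V (Inclusion criteria, 2nd questionnaire) requires "Patient with a VAS score during the 1st assessment" of at least 4/10, plus agreement to change to the gel protocol. Section IV.A (Course of the study) describes the part 2 cohort as patients who reach that threshold "and who wish to switch to the enhanced anesthesia protocol". Section V (Number of interviewees) expects about 300 patients in part 1. Part 2 takes those with severe pain "who consent to test another protocol (estimate: 40 to 60 patients").

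**Main criterion.** Section III defines it as "Comparison of the pain score felt during the injection during the 1st evaluation" against the score under the improved anaesthesia. Section IV.B (Statistical data analysis) names the test: "Comparison of the score obtained during the 1st evaluation (with conventional anesthesia) with the score obtained during improved anesthesia: paired T-test".

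**Which score triggers entry.** Each session yields "2 measures for pain assessment using VAS", one for blepharostat placement and one for needle insertion. The inclusion criterion does not say which must reach 4. Section II speaks of the "management of patients complaining of severe pain during the injection", which leans towards the needle score but does not settle it. The list of questionnaire answers also describes the second-questionnaire patients as scoring above 4, where other sections say 4 or more.

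**Other analyses.** These are a paired t-test on the HAD scores, an unspecified multivariate analysis on psychological state, injection site, number of prior injections, sex and age, and "Confirmation of pain relief with the score obtained on the simple verbal scale". The protocol states no alpha, power, SD or expected effect. It describes no control group and no second score under the reference method, and it does not mention regression to the mean.

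**The concern.** A VAS score varies from one session to the next within the same patient. Patients picked because one score was high include some whose score was high by chance that day, and on average they score lower next time under any anaesthesia. Here the session that selects also supplies the starting value, so part of any fall is built in by the design.

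The other planned analyses do not repair this. The HAD comparison and the multivariate factors do not address selection on the first score. The verbal relief score is collected only at session 2 and has no control either.

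The main objective is to assess the relief that the gel adds to the reference method. Section II itself cites a health-authority opinion that the gel offers no improvement over anaesthetic drops. A significant t-test produced by selection would appear to contradict that opinion without evidence about the gel.

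**Working it through.** **Plan's own figure.** There is no sample-size calculation to reproduce. The only arithmetic available is 40/300 = 13.3% and 60/300 = 20.0%. This is a lower bound on the share scoring 4 or more, because the 40 to 60 are qualifiers who also consent.

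**Inputs from the protocol.** Threshold 4; n = 40 to 60; paired t-test.

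**Inputs assumed.** Two-sided 5% (2.5% in the direction of relief); zero gel effect; mean, SD and qualifying share of the VAS; correlation rho between sessions under the reference method.

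**Step 1: closed form, entry on the needle score.** Take equal means and SDs in both sessions, bivariate normal, mean 2.0 and 20% scoring 4 or more.

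- SD = (4 − 2.0)/0.842 = 2.38.
- Mean excess of the selected, in SD units: λ = φ(0.842)/0.20 = 1.40. Their mean first score is 2.0 + 2.38 × 1.40 = 5.33.
- Expected fall with an inert gel = (1 − rho) × SD × λ = (1 − rho) × 3.33.
- SD of the paired difference = SD × √[(1 − rho)² × 0.219 + 1 − rho²], where 0.219 = 1 + 0.842λ − λ².

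| rho | Null fall (points) | SD of difference | Fall/SE, n=40 | Relief declared, n=40 | n=60 |
|---|---|---|---|---|---|
| 0.5 | 1.66 | 2.13 | 4.93 | 99.9% | 100% |
| 0.7 | 1.00 | 1.73 | 3.65 | 95% | 99% |
| 0.8 | 0.67 | 1.44 | 2.92 | 81% | 94% |
| 0.9 | 0.33 | 1.04 | 2.02 | 52% | 67% |

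The last two columns are simulated.

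**Step 2: bounded scores.** Simulated scores from 0 to 10, rounded to the millimetre, were clipped normal (SD 2) or gamma (shape 1.5), with no session trend.

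| Entry and share qualifying | rho | Null fall (points) | Relief declared, n=40 | n=60 |
|---|---|---|---|---|
| Needle, 20% | 0.4 | 1.66–2.12 | 100% | 100% |
| Needle, 20% | 0.6 | 1.12–1.48 | 95–99% | 100% |
| Needle, 20% | 0.8 | 0.56–0.75 | 66–80% | 84–93% |
| Needle, 20% | 0.9 | 0.28–0.38 | 38–51% | 53–68% |
| Needle, 40% | 0.4–0.9 | 0.20–1.80 | 23–96% | 32–100% |
| Blepharostat or either, 20–40% per item | 0.4–0.9 | 0.10–1.59 | 9–99% | 11–100% |

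The last row falls to about 5% (n about 50) if the two scores share little within-session variation. Sections IV.B and the data list give the VAS as 1 to 10. With a floor of 1, needle entry at 20% gives 41–100% at n = 40, against 38–100% with a floor of 0.

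**Step 3: session trend.** With needle entry, 20% qualifying and n = 40, a 0.5-point rise in pain between sessions leaves 65–97% at rho 0.4–0.6. It cuts this to 4–15% at rho 0.8. At rho 0.9 the fall reverses (−0.22 to −0.09 points) and relief is declared in 0–1%. A 0.5-point fall gives 78–100% for needle entry. The rise needed to cancel the artefact is about the size of the null fall.

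**The case against.** **The size is not known.** This stands. Every distributional input is assumed, and the results run from near nominal to 100%. A reader might infer that a significant result would be entirely artefact, or that the bias always favours the gel. The protocol supports neither: a rise in pain between sessions can cancel or reverse the effect. Section IV.B lists prior injections as related to pain but gives no direction. Acceptance matters too. If patients with higher usual pain accept the gel more often, needle entry gives 5–100% (n about 50).

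**The selecting score may not be the starting score.** This also stands. With blepharostat entry and the needle score analysed, they differ. One may therefore say only that the same session selects and supplies the starting value. The bias is then smaller, with the same direction while the two scores correlate positively within a session.

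**The bias could be estimated from data already collected.** In part. A model using the roughly 300 part 1 scores can adjust for it under assumptions, so it would be too strong to say that the study can never estimate it. The accurate statement is that the planned analysis does not.

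**If so, the adjusted model should become the main test.** This is tempting but goes too far. The model estimates the effect at the part 1 mean, below the cut-off, whereas the objective concerns patients with severe pain. Suppose the gel cuts pain by 30% (normal scores, 20% qualifying, rho 0.9). The selected patients start at 5.07 and would score about 5.07 − 0.28 = 4.79 without the gel, so the true effect is 0.30 × 4.79 = 1.44. The model returned 0.74, close to 30% of the part 1 mean of about 2.4. It can also miss real benefit: power for a true 1.5-point effect can fall to 4% when acceptance rises with usual pain.

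**Conclusion.** The concern holds. Selection on the first session, reuse of that session as the starting value, and the absence of a control or correction are all plain in the protocol. Absent an offsetting session trend, the main test is biased towards relief, so its p-value cannot be read as evidence that the gel works.

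Confidence is high for the direction under that condition and low for the size. With needle entry, acceptance unrelated to usual pain, rho 0.4 to 0.9 and 20% to 40% qualifying, an inert gel produces a fall of about 0.2 to 2.1 points and false relief in about 23% to 100% of studies of 40 patients. These figures show scale; they do not estimate the bias in this study. The result matters because it bears on the only test planned for the main objective.

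**What to change.** 1. **State which VAS triggers entry**, and reconcile the two wordings of the threshold.
2. **Report the paired change with its confidence interval as descriptive.** Do not read the t-test p-value as evidence that the gel relieves pain.
3. **Add a supporting analysis**, not a replacement main test: a regression-to-the-mean-adjusted estimate of the Mee-Chua type.
   - In gel patients, regress the session-2 VAS on the first-session VAS centred at the part 1 mean of all patients (about 300). The estimate is the part 1 mean minus the intercept, with an SE that carries the uncertainty of the part 1 mean.
   - If entry is on the blepharostat VAS or either VAS, include both first-session scores, each centred at its own part 1 mean.
   - State that it estimates the effect at the part 1 mean, and equals the effect in patients with severe pain only if the gel effect does not depend on baseline pain.
   - State that it also assumes linearity, no session effect and acceptance unrelated to usual pain.
   - Show it over a range of assumed session shifts in both directions.
4. **Word the conclusion** as an open-label, uncontrolled before-after difference in patients selected for a high first score, which may include regression to the mean, session and expectation effects.

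**Cost.** Items 1 and 4 are wording. Items 2 and 3 need a small analysis amendment, with no new data, visit or patient. The main result becomes less favourable. The supporting estimate is imprecise: power for a constant 1.5-point effect is about 45–100% at n = 40 (needle entry, normal scores), and lower in less favourable scenarios. It does not remove a session effect: an unadjusted 0.5-point fall gave 5–93% false positives in simulations with about 50–85 gel patients.

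**Optional, not required.** A second VAS under the reference method, from patients who stay on it, would address a session effect. It needs an amendment and follow-up to the next injection, about 2 months on average, against a report planned for August 2022. With needle entry and only below-threshold patients as controls, it would extrapolate across the cut-off.

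### A paired t-test of difference cannot validate that the HAD score is stable, and the plan sets no margin, confidence interval or decision rule that could

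*Combined protocol and SAP*

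**What the plan says.** In Section III, secondary objective 3 is "Description of the psychological state of the patient during a IVT and validation of score stability". The matching criterion is "Descriptive statistics of the psychological state of the study population. Comparison of the scores obtained between the 2 assessments".

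In Section IV.B, under Statistical data analysis, that comparison becomes "Comparison of the scores obtained between the 2 evaluations of the psychological state (HAD scale): paired t-test". Quantitative variables are to be presented "As mean +- sd (min; max) for quantitative variables", so no confidence interval is planned. Nothing in the document gives a significance level, an equivalence margin, an agreement measure or a rule for declaring the score stable.

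The number of pairs comes from Section V, Number of interviewees: patients with severe pain "who consent to test another protocol (estimate: 40 to 60 patients". This is a recruitment estimate, not a calculated sample size.

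**The concern.** The paired t-test takes no mean change as its null hypothesis. Rejecting it is evidence of change. Failing to reject it may mean that the score is stable, or that the study was too small or the score too variable to show a shift. The objective needs the second kind of conclusion (no important change), and the planned test supports only the first.

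This bears on how the main result is read. The pain comparison is before-after in the same patients, without a concurrent control. The protocol gives its reason for measuring the HAD at both sessions: "Pain being strongly correlated with the psychological state of the patient". The second HAD is "completed by the patient before IVT", by "Patients who have given their consent to switch to the protocol with the addition of lidocaine gel". These patients know that their anesthesia is about to change, so a shift in anxiety between sessions is plausible. If the report calls the score stable because p > 0.05, readers may discount anxiety as a contributor to the pain change when the data do not justify it.

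**Working it through.** The plan states no sample size calculation, power or margin for the HAD comparison, so there is no figure to reproduce. The figures below illustrate what the planned test can and cannot show.

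**Inputs**
- Pairs: n = 40 to 60 (Section V, Number of interviewees).
- SD of the within-patient HAD change: not in the documents; assumed 2.5, 3 or 4 points.
- Significance level: not stated; assumed two-sided 0.05 for the t-test and 0.05 per side for two one-sided tests (TOST).
- True shifts of 0, 1 and 1.5 points and margins of ±1, ±1.5 and ±2 points are illustrations, not recommendations.

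**1. How often a real shift gives p > 0.05**

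For true shift δ, the paired t statistic is non-central t with n − 1 degrees of freedom and non-centrality δ√n/SD. For δ = 1, SD = 3, n = 40 this is √40/3 = 2.11 against a critical value of 2.023, and the probability of non-significance is 46%.

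| SD | n = 40, 1 point | n = 60, 1 point | n = 40, 1.5 points | n = 60, 1.5 points |
|---|---|---|---|---|
| 2.5 | 31% | 14% | 4% | 0.5% |
| 3 | 46% | 28% | 13% | 3% |
| 4 | 66% | 52% | 36% | 18% |

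**2. What p > 0.05 does rule out**

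A non-significant result means that the observed mean change is below t(0.975, n−1) × SD/√n. The 90% interval then adds t(0.95, n−1) × SD/√n. The furthest limit still compatible with p > 0.05 is therefore

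[t(0.975, n−1) + t(0.95, n−1)] × SD/√n.

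- n = 40: (2.023 + 1.685)/√40 = 0.586, giving 1.47, 1.76 and 2.34 points for SD 2.5, 3 and 4.
- n = 60: (2.001 + 1.671)/√60 = 0.474, giving 1.19, 1.42 and 1.90 points.

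So a non-significant test does bound the shift. Whether the bound is tight enough depends on a margin that the plan does not set.

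**3. How often the t-test and a margin rule disagree**

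Simulation, 400,000 trials per cell, normally distributed changes. The margin rule requires the 90% interval to lie inside the margin.

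| Situation | n = 40 (SD 2.5 / 3 / 4) | n = 60 (SD 2.5 / 3 / 4) |
|---|---|---|
| No true shift: p > 0.05 but interval not inside ±1 | 35% / 62% / 92% | 11% / 32% / 74% |
| No true shift: p > 0.05 but interval not inside ±2 | 0% / 0.1% / 10% | 0% / 0% / 0.5% |
| True 1-point shift: p < 0.05 although interval inside ±2 | 49% / 21% / 1% | 78% / 54% / 11% |

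The disagreement runs both ways. The t-test can pass where a margin rule would not, and it can flag a change that a wider margin would accept. The fault is therefore the missing criterion, and not only low power.

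**4. Power of the margin rule when there is no true shift**

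| Margin | n = 40 (SD 2.5 / 3 / 4) | n = 60 (SD 2.5 / 3 / 4) |
|---|---|---|
| ±1 | 60% / 33% / 3% | 84% / 64% / 21% |
| ±1.5 | 96% / 86% / 51% | 99.7% / 97% / 78% |
| ±2 | 86% or more | 86% or more |

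**The case against.** **The plan never says that p > 0.05 will be read as stable.** True. The written criterion asks only for descriptive statistics and a comparison, which a paired t-test delivers, and the text reads as a translation, so validation may have meant little more than a check. But as written the objective promises validation, and the plan offers no other basis for it. The harm depends on how the result is reported, and the wording should close off that reading.

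**A second analysis touches psychological state.** The same block lists it among factors correlated with the result and ends with a multivariate analysis of pain scores, so readers may have more than one p-value when judging the role of anxiety. That softens the consequence. The model has pain as its outcome, however, and its patient set and HAD variable are unspecified, so it cannot show that the HAD score was stable.

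**The interval could be recovered.** It could, from the paired means, n and an exact p-value. The plan commits to neither an exact p-value nor means on the paired subset.

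**The HAD score is in effect named.** The questionnaire descriptions call it an anxiety scale, which points to the anxiety subscale. The full title covers depression too, and the analysis section says only HAD scale, so some ambiguity remains.

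**The size rests on assumptions.** It does. The rates vary widely with SD, shift and margin, and with no true shift the two rules almost always agree at ±2 points. The numbers do not show that this trial will probably mislead. The logical gap needs no SD.

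**Conclusion.** The concern holds. The test the plan specifies cannot by itself support the conclusion that objective 3 promises, and nothing else in the document supplies a criterion for stability. That part rests on the text alone, and confidence in it is high.

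The practical size is conditional on the assumed SD, the 0.05 level and whatever margin would be clinically acceptable. At the expected numbers, a 1-point mean shift could easily go undetected; a 1.5-point shift is much less likely to be missed if the SD is near 2.5.

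The objective is secondary. The primary paired t-test on pain is not affected, and even a well-shown stability of HAD would not replace a control group. The change should be made, but it does not threaten the main analysis.

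**What to change.** In the Statistical data analysis section:

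- Name the HAD score to be compared (anxiety, depression or total).
- Report its mean within-patient change with a confidence interval.
- State that p > 0.05 will not be taken as evidence of stability.

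Then choose one of two routes:

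1. **Keep the validation claim.** Fix a clinically justified margin before the data are seen, and claim stability only if the 90% interval for the mean change lies wholly inside it (two one-sided tests).
2. **Drop the validation claim.** If no margin can be justified, reword objective 3 as a description of the change in HAD score, and report the change with its interval.

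An intraclass correlation is optional and describes within-patient agreement only. A regression of pain change on HAD change is not required. If it is run, label it exploratory: the HAD change may itself result from knowing about the switch to gel, so the model could over-adjust as well as under-adjust.

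The cost is a few sentences of analysis plan and a few lines of R, with no new data. Route 1 obliges the sponsor to defend a margin, and it may end in stability not shown, especially with a tight margin. The margin must be justified clinically and not chosen for power. Route 2 costs only the word validation.
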